Consistent with these findings from structural imaging, Menke and colleagues^[24] found in a functional imaging study that greater naming improvement immediately post-treatment was associated with activations in the hippocampus and some right-hemisphere areas (precuneus and cingulate). They also found that naming improvements maintained at 8-month follow-up were associated with increased activity in the right Wernicke's area homologue, and less strongly in left peri-lesional areas. Also consistent with these findings, Crosson and colleagues^[25] found that a group of 4 individuals with aphasia whose naming function improved in response to treatment exhibited more right lateralized activation immediately post-treatment, compared to a patient who did not improve. Parallel functional imaging work by Fridriksson and colleagues has found that successful naming performance by individuals with aphasia is associated with greater activation of either peri-lesional left hemisphere tissue or unaffected right-hemisphere tissue^[73, 74]. These findings strongly suggest that right hemisphere and perilesional left hemisphere tissue can play a critical role in successful treatment response.

A second line of evidence suggests that the hippocampus may play a role in treatment-induced recovery from aphasia. As noted above, Menke and colleagues^[24] found that naming improvement was associated with increased activation in the hippocampus. Parallel to this finding, Meinzer and colleagues^[20] found that improvement on treated object naming items among 10 patients with mild to moderate chronic aphasia was negatively correlated with damage to the hippocampus. Volume loss to the left hippocampus was negatively correlated (-0.65) with improvement on treated items immediately after training, and even more strongly negatively correlated (-0.80) at 8-month follow-up. Loss of integrity of left hippocampus-adjacent white matter tracts (measured using fractional anisotropy maps) was negatively correlated with naming improvement after treatment (-.85) and at follow-up (-0.83). These relationships were specific to treated items: while there was some generalization of treatment effects to untreated items, these effects did not correlate with the structural measures of the hippocampus. This evidence suggests that the hippocampus, which is critical for formation and consolidation of episodic memory, is critical for supporting treatment-related aphasia recovery.

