Some participants may also have co-occurring conditions which would prevent them from participation in the imaging arm of the study (claustrophobia; presence of metal in the body). These participants will be enrolled in the study but will not complete imaging procedures. A chart review of PIRATE participants to date indicates that approximately 20% of veterans enrolled in PIRATE may have such exclusionary criteria: roughly 17% report pacemaker or other implanted metal objects or devices incompatible with MR scanning. Thus, the participant sample used to address the neuroanatomical hypotheses proposed under Specific Aim 1 may be smaller than the sample contributing data the other proposed analyses. Under the worst case scenario of no overlap between these imaging-related exclusionary criteria and those described in the preceding paragraph, we expect to obtain a sample size of 40 participants (50 minus 20%) to conduct the proposed imaging-related analyses. As described in section C.3.1.3 below, this sample size should be sufficient to detect the relationships relevant to the neuroanatomical hypotheses.

C.2 Procedures

The schedule of procedures for participants enrolling in the study is summarized in the flowchart in Figure 4. Participants enrolling in the research study will receive a single pre-treatment structural MRI and a battery of cognitive assessments at program entry (see section C.2.3 below). They will also have their performance on standardized measures of naming and other language functions assessed repeatedly throughout the protocol (see section C.2.2 below), and they will receive an intensive dose of a treatment (SFA) designed to target lexical-semantic processes (see section C.2.1 below). Participants' performance on treated and untreated lexical items will be probed three times weekly, to assess acquisition and generalization and to decide when participants will move to a novel set of treatment exemplars.

Half the participants will be randomly assigned to a delayed-treatment condition. The purpose of this condition is to provide an additional measure of experimental control, to ensure that any observed improvements are not due simply to the social contact afforded by the residential component of the treatment program. Previous work [7] has found that simple exposure or engagement in the absence of specific therapy

[figure not shown]

Figure 4: Testing and treatment procedures for study participants

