VLSM analysis will proceed in several steps. First, we will employ a multi-step lesion tracing procedure, first tracing lesions volume-by-volume in a descending axial plane while simultaneously referencing the coronal and sagittal views in the ITK-Snap image processing program^[105]. These initial tracings will be conducted via consensus among study staff. We will then subject these initial tracings to a second round of consensus with different raters and conduct minor adjustments as needed. [name] will have final say in any conflicts regarding lesion tracing. He will also be blind to each participant's corresponding behavioral data.

Upon reaching consensus on the lesion distributions, we will warp the original brains and their respective lesion masks into a standard neurological space (i.e., Montreal Neurological Institute template). We will first re-align each brain along its AC-PC axis and then segment it into distinct tissue types (i.e., gray matter, white matter, CSF, skull). After these initial pre-processing steps, we will normalize each brain using SPM-08. During normalization, we will apply the lesion tracings as masks with the goal of preventing tissue distortion in and around the lesion. We will then apply the original normalization parameters to the masks themselves in order to derive a set of normalized lesion patterns that may then be overlaid on a canonical brain and contrasted across subjects.

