We will use the MRICron program's nonparametric lesion mapping (NPM) feature to complete the lesion symptom correlations^[106]. These data will be structured such that there is a binary classification at the voxel level (i.e., ±lesion) and continuous behavioral data (change score associated with the different outcome measures: PNT scores and scores on acquisition/generalization probes). Since these data are likely not to satisfy parametric statistical assumptions, we will use the NPM program's Brunner-Munzel nonparametric test to relate behavioral performance on each of the treatment-outcome predictors (change scores) to lesion distributions^[107-109]. We will apply a cluster threshold of 10 contiguous voxels and threshold for a false discovery rate of .05 in order to control for type I error while maintaining sufficient power to detect effects. We will also include voxels that have at least a 25% lesion overlap across patients. VLSM analyses will focus on four principal regions of interest (ROIs): left anterior cortex, left posterior cortex, left basal ganglia, and left hippocampus. Previous work (reviewed in section B.2 above) has shown that positive response to aphasia treatment is associated with intact left hippocampus and left basal ganglia. In addition, some previous work suggests that negative treatment response is associated with more intact left anterior cortex^[21], but other work suggests that greater recruitment of left anterior cortex is associated with positive treatment response^[23]. Additional work has also found that more intact left posterior cortex is associated with more positive treatment response^[23].

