Change scores from program entry to program exit and/or follow-up will be computed for primary and secondary study measures: weekly PNT scores and acquisition/generalization probes. These scores will be correlated with lesion extent using VLSM, with analysis focusing on the four ROIs identified above. These correlations will serve to test the hypotheses relevant to Specific Aim 1 above. As predicted by Hypothesis 1c and consistent with the preliminary findings from the PIRATE participants (see B.2.1 above), we anticipate that there will be a significant negative correlation between change scores and lesion extent in left basal ganglia and hippocampus. Greater damage to structures required for learning and memory function (hippocampus) and to structures which can control maladaptive activation of damaged left-hemisphere tissue (basal ganglia) will result in poorer treatment outcomes. Also as predicted by Hypothesis 1c and consistent with preliminary data by Parkinson and colleagues (see B.2.1), we anticipate that extent of left-anterior hemisphere lesion will be positively correlated with change scores. Greater damage to left anterior cortex will prompt greater recruitment of right hemisphere cortex or other non-lesioned left hemisphere cortex, resulting in more positive treatment outcomes^[20, 25]. Furthermore, we anticipate that extent of left posterior cortex will be associated with poorer treatment outcomes, given Fridriksson's findings^[23].

Additional exploratory analyses will be carried out to examine how these neuroanatomical factors predict performance for the different outcome measures. We anticipate that brain regions which are positively correlated with change scores for acquisition probes will not be positively correlated with change scores for generalization probes, given the behavioral^[9] and neuroimaging evidence^[20] that treatment response for treated and untreated items/behaviors leans on different cognitive and neural mechanisms. We do not have any a priori predictions regarding what brain regions may be correlated with change scores for generalization probes.

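### The 25% lesion-overlap rule can leave a hypothesised region such as the hippocampus with no voxel to test, and the plan states no regional test in its place

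*Combined protocol and SAP*

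**What the plan says.** Section C.3.1.3 structures the lesion data so that "there is a binary classification at the voxel level (i.e., ±lesion) and continuous behavioral data", and relates the two with the Brunner-Munzel test at each voxel. It states "We will also include voxels that have at least a 25% lesion overlap across patients", applies a cluster threshold of 10 contiguous voxels, and will "threshold for a false discovery rate of .05 in order to control for type I error". The analysis focuses on "left anterior cortex, left posterior cortex, left basal ganglia, and left hippocampus". On numbers, section C.1 says "we expect to obtain a sample size of 40 participants (50 minus 20%) to conduct the proposed imaging-related analyses".

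The predictions in the same section are about regions, not voxels. Under Hypothesis 1c it anticipates "a significant negative correlation between change scores and lesion extent in left basal ganglia and hippocampus", and a positive correlation with the extent of left anterior damage. A further prediction, poorer outcome with left posterior damage, is added on the strength of a separate cited study. The section says that the VLSM correlations are what will test these hypotheses. If the regions show no significant correlations, the plan moves to VLSM in subgroups, divided by aphasia severity.

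The structural evidence on the hippocampus in section A.2.2 comes from a study of 10 patients: "Volume loss to the left hippocampus was negatively correlated (-0.65) with improvement on treated items immediately after training". The same study reports a relation with the integrity of adjacent white matter.

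**The concern.** The hypothesis and the test are on different scales. The hypothesis concerns how much of a named region is damaged. The test asks, voxel by voxel, whether lesioned participants changed more or less than unlesioned ones, and only where enough participants are lesioned. A region in which no voxel reaches the overlap threshold contributes nothing, so its prediction is never examined. This is more of a risk for a small structure, where damage may be uncommon or may fall in different parts in different people. A region could be damaged in ten or more participants overall and still have no single voxel damaged in ten.

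The plan has no step that checks whether each region has eligible voxels, and no label for one that has none. Readers of the results could not tell a prediction that was tested and not supported from one that was not tested. What is at stake is the interpretability of part of Specific Aim 1.

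**Working it through.** **Inputs.** Scanned participants: 40 (section C.1, 50 minus 20%). Overlap threshold: 25% (section C.3.1.3). Share of participants lesioned at a hippocampal voxel: not given in the text available, so varied as an assumption.

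**The plan's own figure.** Section C.3.1.3 states power of 0.80 at n = 40 for correlations of 0.38 or more, and above 0.99 for 0.65 to 0.85. For one Pearson correlation by Fisher z, power is Φ(atanh(r)·√(n − 3) − z).

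- r = 0.38: atanh(0.38)·√37 = 0.400 × 6.083 = 2.43. One-sided 5%: Φ(2.43 − 1.645) = 0.785; simulation gives 0.795. Two-sided 5%: Φ(2.43 − 1.96) = 0.68.
- r = 0.65: one-sided 0.999, two-sided 0.997.

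The stated figures are therefore reproduced if the test is one-sided, which the plan does not say. They describe a single correlation that uses all 40 participants. They take no account of the overlap rule, the binary predictor or the false discovery rate threshold, so they give no assurance that any hippocampal voxel will be tested.

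**The overlap rule.** 0.25 × 40 = 10 participants lesioned at the same voxel. With true share p, the chance that a given voxel qualifies is the binomial tail P(X ≥ 10 | 40, p):

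| Assumed true share p | Expected lesioned, 40p | Voxel qualifies | Voxel not tested |
|---|---|---|---|
| 5% | 2 | <0.001 | >0.999 |
| 10% | 4 | 0.005 | 0.995 |
| 15% | 6 | 0.067 | 0.933 |
| 20% | 8 | 0.268 | 0.732 |
| 25% | 10 | 0.560 | 0.440 |
| 30% | 12 | 0.804 | 0.196 |
| 40% | 16 | 0.984 | 0.016 |

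These are per-voxel figures. A region holds many correlated voxels, so the chance that at least one qualifies is higher; a reported finding still needs 10 contiguous voxels.

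**The subgroup fallback.** The rule is a percentage, so a subgroup of 20 needs 0.25 × 20 = 5. At shares of 10%, 15%, 20% and 25% the chance of qualifying is 0.043, 0.170, 0.370 and 0.585, against 0.005, 0.067, 0.268 and 0.560 in all 40.

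**A regional measure.** One correlation per region uses all 40 participants, whatever the voxel overlap. Two-sided 5% power is 0.68, 0.92 and 0.997 at r = 0.38, 0.50 and 0.65. With Bonferroni over four regions (two-sided 0.0125) it is 0.47, 0.80 and 0.99. These are Pearson figures; a rank correlation with many tied zeros would have less.

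**The case against.** Several points on the other side have force.

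- **Missing frequency.** Part of the Preliminary Studies section was not in the text available, and C.3.1.3 refers to pilot findings in a section B.2.1 that is not there. The absence of a lesion frequency cannot be held against the plan. It only means that the risk must be shown over a range.
- **Size.** Over shares of 10% to 30% the qualifying probability runs from 0.5% to 80%, driven by the assumption, and it is per voxel. It shows that a region can drop out, not that it will.
- **Wording.** The plan says that lesion size and extent will be quantified, predicts correlations with extent, and computes power for a correlation. A regional measure may have been intended. But the only procedure described is the voxelwise one. The rule is also phrased as voxels that will be included rather than as a limit; a floor is the natural reading, since a 25% threshold otherwise does nothing.

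Four stronger readings are tempting, and the documents do not support them.

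- A reader might infer that an untested region will be reported as showing no correlation. C.3.1.3 does not say so: its contingency refers to the regions together and says nothing about reporting. The defect is that no category exists for an untested region.
- A reader might infer that the subgroup step makes the mask stricter. At shares of 10% to 25% a voxel qualifies more often in a subgroup of 20, although fewer lesioned participants then support each test.
- A reader might take all four regions as part of Hypothesis 1c. C.3.1.3 ties only the basal ganglia, hippocampus and left anterior cortex to it explicitly.
- A reader might conclude that hippocampal volume should replace lesion extent because the cited evidence concerns volume. Volume is a different predictor from the one hypothesised, and the planned segmentation into tissue types does not delineate the hippocampus.

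**Conclusion.** The concern holds in a limited form. The only stated test of four regional predictions is restricted to voxels lesioned in at least 10 of about 40 participants, so a region without such voxels is not tested, and the plan does not distinguish that from a non-significant result. The threshold of 10 follows directly from the plan's figures and the reading of the 25% rule as a floor. How likely a drop-out is cannot be settled from the text available. A given voxel is more likely than not to be excluded at an assumed share of 20% or less, close to even at 25%, and usually included at 30% or more; for a whole region the chance of exclusion is lower than for one voxel. The mismatch between regional extent and voxelwise status stands whatever the frequency, and can be corrected at little cost.

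**What to change.** Amend C.3.1.3 as follows.

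1. For each of the four regions, compute the proportion of the region lesioned from the normalised masks, for every scanned participant. Test it against the primary change score (treated items, exit minus entry) by a rank correlation, with a stated multiplicity correction over the four regions. Fix the region boundaries in template space in advance.
2. Keep the 25% rule for the voxel map only.
3. For each region, report how many participants had any lesion there and how many voxels were tested. Label a region with no eligible voxels 'not tested' in the voxel map.
4. Optionally, add left hippocampal volume from the T1 scan as a secondary exploratory measure. It is closer to the evidence in section A.2.2.

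The cost is SAP wording and one derived variable per region; items 1 to 3 need no new scans or visits. Hippocampal volume would need an extra delineation step and a visual check where the lesion touches the structure. The downsides are four added tests, and a regional share that is mostly zero if few participants are lesioned there. That should be reported as limited information about the region, not as evidence against the prediction.

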The first analysis will evaluate whether the social contact associated with PIRATE participation results in improved performance on study measures, independent of any actual aphasia treatment. We will use a multivariate mixed model to test whether there are any differences between the immediate-treatment and delayed-treatment groups at the initiation of treatment, and whether there is any group-by-time interaction suggesting a positive effect of the delayed treatment week. The dependent variables will include performance on treated and untreated naming probes and PNT short forms.

If this analysis finds no significant differences between the groups, it will suggest that any observed treatment gains can be attributed to the SFA treatment rather than general effects of the social contact associated with PIRATE. In this case, the two groups will be collapsed for further analysis. In the unexpected event that this analysis finds a significant difference favoring the delayed treatment condition, it will suggest that observed treatment gains should be attributed to the combination of SFA and the socialization inherent in a residential treatment program, rather than to SFA alone. In this case, we will use the data to estimate the size of the socialization effect and statistically control for it in subsequent analyses, where possible.

C.3.1 Psycholinguistic, cognitive, and neuroanatomical predictors of treatment response

The primary dependent variable for analyses relevant to Specific Aim 1 will be the proportion of correctly-named treated stimuli at study exit (post-treatment), minus the proportion of correctly-named treated stimuli at study entry (pre-treatment). This difference score provides the simplest measure of naming treatment response. Supplementary analyses may be carried out using a related dependent variable, the percentage of possible naming improvement^[10]. This is a derived measure which divides the simple pre-post difference score

by the difference between pre-treatment naming performance and ceiling performance (100% accuracy minus observed pre-treatment accuracy). This measure helps correct for observed differences in baseline accuracy.

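### The lesion analysis for Hypothesis 1c does not name the outcome and time point that decide it, nor say whether the FDR of .05 covers one map or all

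*Combined protocol and SAP*

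**What the plan says.** **Aim 1 outcomes (C.3.1).** "The primary dependent variable for analyses relevant to Specific Aim 1 will be the proportion of correctly-named treated stimuli at study exit (post-treatment"), less the same proportion at entry. The secondary outcomes, untreated related items and the Rasch-scaled PNT score, are also defined as exit minus entry.

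**Lesion analysis (C.3.1.3).** The Brunner-Munzel test is used to "relate behavioral performance on each of the treatment-outcome predictors (change scores) to lesion distributions". The error control is a 10-voxel cluster threshold and a "threshold for a false discovery rate of .05". Four left-hemisphere regions of interest are named. The change scores are then described: "Change scores from program entry to program exit and/or follow-up will be computed for primary and secondary study measures", meaning "weekly PNT scores and acquisition/generalization probes". Of the results the section says: "These correlations will serve to test the hypotheses relevant to Specific Aim 1 above".

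**Predictions in the same section.** Greater damage to basal ganglia, hippocampus and posterior cortex should go with poorer response, and greater anterior damage with better response. For generalization probes no region is predicted in advance, and the comparison of predictors across outcome measures is called exploratory.

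**If nothing is found.** C.3.1.3 adds lesion analyses in subgroups, but only when no region correlates significantly with change on the outcome measures.

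**The concern.** Three things are left open where the plan says how Hypothesis 1c is tested.

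1. **Time point.** The Aim 1 outcomes end at exit. The lesion analysis admits exit, follow-up or both, with no rule if they disagree.
2. **Deciding score.** The text refers to primary and secondary measures but does not say that the primary one settles the hypothesis. The subgroup fallback points the other way, since it treats the main analysis as empty only if no measure shows anything.
3. **Scope of the FDR.** One rate is given. Nothing says whether it applies within each map or over all of them, and no control across measures or time points is stated.

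Disagreement between maps is foreseeable. The plan's own background (A.2.2) describes one study in which immediate and 8-month gains were linked to different areas, and another in which hippocampal measures tracked gains on treated but not untreated items. As written, a region that passes threshold on any one map could be reported as support for Hypothesis 1c. The chance of a false region is then higher than .05 suggests.

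**Working it through.** **The plan's own figure.** C.3.1.3 gives power 0.80 for r = 0.38 with n = 40, without stating alpha or sidedness. By Fisher's z, power = Φ(atanh(r)·√(n − 3) − z).
- atanh(0.38)·√37 = 0.400 × 6.083 = 2.434.
- One-sided .05: Φ(2.434 − 1.645) = 0.785 (simulation 0.794), within two points of 0.80.
- Two-sided .05: Φ(2.434 − 1.960) = 0.682, which does not match.

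The stated power therefore corresponds to one correlation at one-sided .05. It allows neither for voxel-wise thresholding nor for several maps.

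**How many maps carry a prediction.**
- Treated items at exit and at follow-up: two. C.2.2 schedules the probes at both.
- PNT at exit: one.
- PNT at follow-up: uncertain. C.2.2 schedules the PNT in the baseline and treatment phases, while C.3.2 predicts no significant change from exit to follow-up in analyses that include PNT scores.
- Generalization: not counted, because no region is predicted.

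That gives three or four maps.

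**Chance of at least one false-positive map.** Under the global null (no voxel related to any score), FDR .05 within a map is at most a .05 chance of any finding in that map. For k independent maps the chance is 1 − 0.95^k:
- k = 3: 1 − 0.857 = 0.143.
- k = 4: 1 − 0.815 = 0.185.

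Change scores on the same people are correlated, which lowers this. Each map is represented by one standard normal statistic tested at |z| > 1.96. The correlation between measures and the correlation between exit and follow-up are assumed, and their product is used where both differ. Simulation gives:

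| Between measures | Exit to follow-up | Three maps | Four maps |
|---|---|---|---|
| 0 | 0 | 0.143 | 0.185 |
| 0.3 | 0.6 | 0.130 | 0.164 |
| 0.5 | 0.6 | 0.126 | 0.156 |
| 0.5 | 0.8 | 0.117 | 0.139 |
| 0.7 | 0.8 | 0.109 | 0.128 |

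The range is about 0.11 to 0.19, or roughly two to four times 0.05.

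**Predicted direction only.** If a map supports the hypothesis only when the effect has the predicted sign, the single-map rate is 0.025. The same simulation gives 0.055 to 0.074 for three maps and 0.064 to 0.096 for four. The absolute risk is about half, and the relative inflation is similar.

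**Cost of the alternative remedy.** Keeping four maps with Bonferroni (.05/4 = .0125) lowers one-sided power at r = 0.38 from 0.785 to 0.58. The correlation detectable with 80% power rises from 0.39 to 0.47. With one pre-named map, no correction across maps is needed.

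**The case against.** The strongest reply is that the hierarchy already exists. The lesion analysis is a subsection of C.3.1, which ranks the outcomes for all of Aim 1, and C.3.1.3 itself speaks of primary and secondary measures. On that reading only a restatement is missing. This stands in part: the outcome is ranked, and the choice is not wholly free. But the ranking is not tied to the decision on Hypothesis 1c, and it cannot settle the time point, because follow-up lies outside every outcome defined in C.3.1.

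The scope of the FDR is also an inference. The word each in the description of the test suggests one analysis per change score, but the plan does not say that the FDR is applied separately. If it were taken over all maps at once, the inflation calculated here would not arise. An FDR of .05 equals a .05 chance of any false finding only under the global null. The single-statistic model also ignores the 10-voxel cluster threshold.

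The Specific Aims statement, with the wording of Hypothesis 1c, is not in the text available for review and may name the deciding measure. The point therefore concerns the analysis section.

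A reader might infer something stronger: that Hypothesis 1c has six or more tests, each at full alpha, from three measures at two time points (eight maps if unrelated items are mapped). For six maps the same method gives about 0.17 to 0.26. The documents do not support that count. Generalization has no regional prediction to confirm, no unrelated-item map is specified, and PNT at follow-up is uncertain. A reader might also infer that follow-up would be brought in once the exit map had been seen. The plan gives no order of analysis: it does not prevent this, but it does not describe it either.

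**Conclusion.** The concern holds in limited form. C.3.1.3 does not carry the Aim 1 hierarchy into the test of Hypothesis 1c, leaves the time point open, and does not give the scope of the FDR. With three or four maps carrying predictions and the FDR applied per map, the chance of at least one false-positive map under the global null is about 0.11 to 0.19 instead of 0.05. Counting only hits in the predicted direction, it is about 0.055 to 0.096 instead of 0.025. These figures assume correlations from 0.7 between measures and 0.8 between time points down to independence, because the documents give none. The inflation is real but moderate, and it can be removed before analysis by a change of wording.

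**What to change.** In C.3.1.3:

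- State that Hypothesis 1c is decided by one analysis: the treated-item change from entry to exit, as C.3.1 defines it.
- State that the FDR of .05 is taken once, over the tested voxels of the four regions of interest together.
- Remove the follow-up option from the sentence that describes this test.
- Label the PNT, generalization and follow-up maps as secondary or exploratory.

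This changes wording only and needs no new data, visits or participants. The downside is that a region found only on a secondary measure or at follow-up would be reported as exploratory.
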